## Overview of Safety Reporting in the Main Study

(a) Refer to Section 10.4.4; eg, this includes AEs related to study procedures which are procedures related to interventions (eg, blood drawn for immunogenicity sampling) that may result in an AE (eg, bruise).

(b) Adverse events of special interest (AESIs that require reporting to the sponsor within 24 hours).

### 8.3.2. Method of Detecting Adverse Events, Medically-attended Adverse Events, Adverse Events of Special Interest, and Serious Adverse Events

Care will be taken not to introduce bias when detecting AEs, MAAEs, suspected AESIs, or SAEs. Open-ended and nonleading verbal questioning of the participant is the preferred method to inquire about AE occurrence.

#### Solicited Adverse Events (Applicable for Double-blind phase only)

Solicited AEs are used to assess the reactogenicity of the study vaccine and are predefined local (at injection site) and systemic events for which the participant is specifically questioned, and which are noted by participants in their e-Diary.

The first 2,000 participants in each of the 2 age groups will remain under observation at the study site for at least 30 minutes post-vaccination to monitor for the development of acute reactions. If at the time of the Day 3 safety review of the initial 2,000 participants no acute reactions have been observed in the age groups, the observation period at the study site may be reduced to at least 15 minutes post-vaccination for the remaining participants in the study.

In addition, participants in the Safety Subset (double-blind phase) will record solicited signs and symptoms in an e-Diary from time of double-blind vaccination until 7 days post-vaccination. Participants in the Safety Subset will be provided with an e-Diary and instructions on how to complete the diary (see Overview in Section 8). Electronic diary information will be transferred

from the e-Diary source to the sponsor. After review and verbal discussion of the initial e-Diary entries with the participant, the investigator will complete his/her own assessment in the relevant sections of the eCRF/eCOA. Once a solicited sign or symptom from an e-Diary is considered to be of severity Grade 1 or above, it will be recorded as a solicited AE.

### ***Solicited Injection Site (Local) Adverse Events***

Participants will be asked to note in the e-Diary occurrences of injection site pain/tenderness, erythema, and swelling at the study vaccine injection site daily for 7 days post-vaccination (day of vaccination and the subsequent 7 days). The extent (largest diameter) of any erythema and swelling should be measured (using the ruler supplied) and recorded daily. The case definitions for solicited injection site events can be found in the references.

### ***Solicited Systemic Adverse Events***

Participants will be instructed on how to record daily temperature using a thermometer provided for home use. Participants should record the temperature in the e-Diary in the evening of the day of vaccination, and then daily for the next 7 days approximately at the same time each day. If more than 1 measurement is made on any given day, the highest temperature of that day will be recorded in the e-Diary.

Fever is defined as endogenous elevation of body temperature  $\geq 38.0^{\circ}\text{C}$  or  $\geq 100.4^{\circ}\text{F}$ , as recorded in at least 1 measurement.

Participants will also be instructed on how to note signs and symptoms in the e-Diary on a daily basis for 7 days post-vaccination (day of vaccination and the subsequent 7 days), for the following events: fatigue, headache, nausea, myalgia.

### **Unsolicited Adverse Events (Applicable for Double-blind phase only)**

Unsolicited AEs are all AEs for which the participant is not specifically questioned.

### **Medically-attended Adverse Events**

MAAEs are AEs with medically-attended visits including hospital, emergency room, urgent care clinic, or other visits to or from medical personnel for any reason. New onset of chronic diseases will be collected as part of the MAAEs. Routine study visits will not be considered medically-attended visits.

For details about AESIs, refer to Section [8.3.7](#).

### **8.3.3. Follow-up of Adverse Events, Medically-attended Adverse Events, Adverse Events of Special Interest, and Serious Adverse Events**

The investigator is obligated to perform or arrange for the conduct of supplemental measurements and evaluations as medically indicated to elucidate the nature and causality of the AE, suspected AESI, MAAE, SAE, or PQC as fully as possible. This may include laboratory tests or investigations, histopathological examinations, or consultation with other HCPs.

AEs, including pregnancy, will be followed by the investigator as specified in [Appendix 4](#).

### **8.3.4. Regulatory Reporting Requirements for Serious Adverse Events**

The sponsor assumes responsibility for appropriate reporting of AEs to the regulatory authorities. The sponsor will also report to the investigator (and the head of the investigational institute where required) all suspected unexpected serious adverse reactions (SUSARs). The investigator (or sponsor where required) must report SUSARs to the appropriate IEC/IRB that approved the protocol unless otherwise required and documented by the IEC/IRB. A SUSAR will be reported to regulatory authorities unblinded. Participating investigators and IEC/IRB will receive a blinded SUSAR summary, unless otherwise specified.

### **8.3.5. Pregnancy**

All initial reports of pregnancy in participants or partners of male participants must be reported to the sponsor by the study-site personnel within 24 hours of their knowledge of the event using the appropriate pregnancy notification form. Abnormal pregnancy outcomes (eg, spontaneous abortion, fetal death, stillbirth, congenital anomalies, ectopic pregnancy) are considered SAEs and must be reported using an SAE reporting form. Any participant who becomes pregnant during the study will remain in the study and will continue to undergo all procedures for surveillance and follow-up of COVID-19 and all safety follow-up as outlined in the protocol for all participants. Participants who are pregnant and received placebo during the double-blind phase may be vaccinated with Ad26.COV2.S if allowed by local regulations and if the investigator considers that the potential benefits outweigh the potential risks to the mother and fetus (See Section [6.4](#)). Participants who are pregnant may receive booster vaccination with Ad26.COV2.S if allowed by local regulations and if the investigator considers that the potential benefits outweigh the potential risks to the mother and fetus (see Section [6.5](#)).

Follow-up information regarding the outcome of the pregnancy and any postnatal sequelae in the infant will be required.

### **8.3.6. Disease-related Events and Disease-related Outcomes Not Qualifying as Adverse Events or Serious Adverse Events**

(S)AEs caused by molecularly confirmed SARS-CoV-2 infection will be removed at the analysis level from the (S)AE listings and tables and presented separately.

All events that meet the definition of an SAE will be reported as SAEs, regardless of whether they are protocol-specific assessments.

### **8.3.7. Adverse Events of Special Interest**

Adverse events of special interest are significant AEs that are judged to be of special interest because of clinical importance, known or suspected class effects, or based on nonclinical signals. Adverse events of special interest will be carefully monitored during the study by the sponsor.

Adverse events of special interest must be reported to the sponsor within 24 hours of awareness irrespective of seriousness (ie, serious and non-serious AEs) or causality following the procedure described above for SAEs.

Specific requirements for the AESI are described below.

### **8.3.7.1. Thrombosis with Thrombocytopenia Syndrome**

As described in Section 2.3.1, Risks Related to Study Participation, TTS has been observed very rarely following vaccination with Ad26.COV2.S and is considered an AESI in this study. TTS is a syndrome characterized by a combination of both a thrombotic event and thrombocytopenia.

Because this syndrome is rare and not completely understood, all cases of thrombosis and/or thrombocytopenia will be considered a suspected case of TTS until further adjudication can be performed. An AESI Adjudication Committee with appropriate expertise will be established to evaluate each suspected AESI and determine whether it is a case of TTS. The investigator shall be responsible for reporting any suspected AESI of TTS using the SAE form and the form detailed in Section 10.13, Appendix 13. A suspected TTS case is defined as:

Thrombotic events: suspected deep vessel venous or arterial thrombotic events as detailed in Section 10.14, Appendix 14

Thrombocytopenia, defined as platelet count below  $150,000/\mu\text{L}^9$  as per the Brighton Collaboration.

Symptoms, signs, or conditions suggestive of a thrombotic event should be recorded and reported as a suspected AESI even if the final or definitive diagnosis has not yet been determined, and alternative diagnoses have not yet been eliminated or shown to be less likely. Follow-up information and final diagnoses, if applicable, should be submitted to the sponsor as soon as they become available.

In the event of thrombocytopenia, study site personnel should report the absolute value for the platelet count and the reference range for the laboratory test used.

For either a thrombotic event or thrombocytopenia, testing for anti-PF4 should be performed at the local laboratory or substitute local laboratory; repeat testing may be requested for confirmation upon sponsor discretion.

Suspected AESIs will require enhanced data collection and evaluation (see Section 1.3.5). Every effort should be made to report as much information as possible about the AESI to the sponsor in a reasonable timeframe.

If an event meets the criteria for an SAE (Section 10.4.1), it should be reported using the same process as for other SAEs.

The form detailed in Section 10.13, Appendix 13 is intended as a guide for assessment of the AESIs to facilitate diagnosis and determine treatment options. If the investigator is not the treating

physician, every effort should be made to collect the information requested in the form from the treating physician and enter the available information in the eCRF.

The sponsor will also attempt to collect information from any thrombotic event /thrombocytopenia/ TTS reported prior to protocol Amendment 5.

#### **8.4. Virology Assessments**

Nasal swabs will be used to detect and/or quantify SARS-CoV-2. Exploratory quantification of the SARS-CoV-2 viral load in saliva samples may also be performed.

Gene sequencing may be performed to detect changes in the S gene and potentially also other parts of the viral genome, if a sample is available.

Up to Amendment 7, nasal swabs collected during a confirmed COVID-19 episode may also be tested at a central laboratory for the presence of other respiratory pathogens using a broad respiratory pathogens panel.

All confirmed COVID-19 episodes will be communicated to the respective participant and to other authorities according to local regulations.

Participants, with stable/well-controlled HIV infection, will be encouraged to have HIV RNA viral load and CD4 cell count assessed at least twice a year and to provide these data for inclusion in the eCRF.

#### **8.5. Biomarkers**

Up to Amendment 7, during a COVID-19-episode, blood will be collected on COVID-19 Day 3-5 and on COVID-19 Day 29 for evaluation of biomarkers (eg, those associated with severe COVID-19).

#### **8.6. Medical Resource Utilization**

As of Amendment 7, this is no longer applicable.

Medical resource utilization data over the last 3 months, associated with medical encounters, will be collected by interview with the participant and recorded in the eCRF by the investigator and study-site personnel at baseline (for all participants, concerning MRU within the last 3 months before double-blind vaccination), and on COVID-19 Day 3-5 and COVID-19 Day 29 (for all participants during a COVID-19 episode; which is defined to be resolved after having 2 consecutive SARS-CoV-2 negative nasal swabs and 2 consecutive days with no COVID-19-related signs or symptoms; see Section 8.1.2]) (Appendix 7). Medical resource utilization data will also be collected through the MA-COV form (Appendix 8). This form will be provided to the participant at the double-blind vaccination visit and should be completed by the medical care provider or the study site personnel during medical visits for COVID-19 or COVID-19 complications. Protocol-mandated procedures, tests, and encounters are excluded. The data collected may be used to conduct exploratory economic analyses and will include:

- Number and duration of medical care encounters, including selected procedures (inpatient and outpatient)
- Duration and type of mechanical ventilation and ECMO use
- Duration of hospitalization (total days length of stay, including duration by wards; eg, ICU)
- Number and character of diagnostic and therapeutic tests and procedures
- Outpatient medical encounters and treatments (including physician or emergency room visits, tests and procedures, and medications)

## 8.7. Risk Factor Assessment

As of Amendment 7, this is no longer applicable.

If allowed by local regulations and if the participant consents, he/she will be interviewed on characteristics related to his/her current work situation, living situation, and community interactions (See [Appendix 12](#)) prior to double-blind vaccination on Day 1 and, at other timepoints, on changes compared to Day 1. These characteristics can potentially be useful to identify the risk of individual participants in acquiring COVID-19 and will be used in several analyses including the correlate analysis.

Risk factor data initially collected from participants at screening prior to implementation of protocol Amendment 3 will also be used for the planned risk-factor analysis.

## 8.8. Participant Medical Information Prior to, During and After the Study (Real-world Data)

For consenting participants in the US, medical data from 5 years prior to study enrollment until 5 years after study completion, such as electronic health records, claims and laboratory data from other care settings may be accessed utilizing tokenization and matching procedures. These data, together with data collected as part of the study as specified in the [Schedules of Activities](#), may be used to conduct exploratory analyses to enhance our understanding of the impact of prior medical history on the response to immunization and the impact of immunization on efficacy and duration of efficacy as well as adverse events that may occur during and after completion of the study (see Section [9.5.4](#)). The utilization of tokenization and matching procedures allows for the medical data to be obtained without violation of participant confidentiality (Section [4.2](#) and [4.2.1](#)). The real-world medical data, which are not collected as part of the study, will not be part of the clinical study database.

## 8.9. Assessment and Procedures After EUA or Approval/Licensure and Implementation of Protocol Amendment 4

Following EUA, conditional licensure, or approval in any country for a single dose regimen based on the VAC31518COV3001 study interim results, all participants from countries where Amendment 4 is approved by the local Health Authority and IEC/IRB will be unblinded at the on-site Month 6/Unblinding Visit. The study will then be conducted in an open-label fashion. A final analysis of the double-blind phase will be performed, using the data collected prior to unblinding,

when all participants have completed the Month 6/Unblinding Visit or discontinued earlier. Depending on the operational implementation of the Month 6/Unblinding Visit, as well as the stage of the pandemic, this analysis may be conducted when a minimum of 90% of the study population has been unblinded.

Participants in the Ad26.COV2.S group will be assured they received at a minimum the dose level that was submitted for EUA approval (single-dose regimen of  $5 \times 10^{10}$  vp Ad26.COV2.S) and will be asked to continue to be followed in this study in line with the [Schedules of Activities](#).

A Month 6/Unblinding Visit will take place for all participants. A nasal swab and blood sample for serology will be collected from all participants. In addition, body temperature and urine pregnancy test (for participants of childbearing potential) will be collected from participants who will be vaccinated at this visit. Participants from placebo group will be offered to receive 1 dose of Ad26.COV2.S vaccine under the conditions delineated in Section [6.4](#). After vaccination, participants should remain under observation at the study site for at least 15 minutes for the presence of any acute reactions after vaccination and will be followed for SAEs until 1 year after Ad26.COV2.S administration.

The importance to continue practicing other public health or preventative measures that were introduced at the start of this pandemic (eg, social distancing, face masks, frequent hand washing), in compliance with local and national guidelines, will be emphasized.

## **8.10. Assessment and Procedures Related to Booster Vaccination**

### **As of Protocol Amendment 7:**

No further booster doses will be administered after implementation of Protocol Amendment 7, except if there is a medical reason that prevented a participant to receive the Ad26COV2.S vaccine prior to acceptance of amendment 7 or if there is a non-availability of other vaccines to the participant. The investigator should inform participants on the availability of other COVID-19 vaccines.

### **Up to Protocol Amendment 7:**

The Year 1/Booster Visit will take place for all ongoing participants. Participants who have previously received any COVID-19 vaccination(s) (as primary regimen or additional dose) with the Ad26.COV2.S vaccine, and/or an mRNA vaccine or another COVID-19 vaccine authorized for primary vaccination including protein, inactivated, and adenovector based vaccines will be offered to receive a 1-dose booster vaccination with Ad26.COV2.S at the  $5 \times 10^{10}$  vp dose level. Participants who choose not to receive booster vaccination at this time will be informed that they can still choose to receive the booster vaccination at a later date within the visit window. In addition, body temperature and urine pregnancy test (for participants of childbearing potential) will be collected from participants who will be vaccinated at this visit. After vaccination, participants should remain under observation at the study site for at least 15 minutes for the presence of any acute reactions after vaccination and will be followed for SAEs until 1 year after Ad26.COV2.S administration.

Participants who choose to receive a booster vaccination outside of the study are encouraged to schedule their Year 1/Booster Visit prior to their booster vaccination, if feasible, and come in for the Year 1 + 28 Days and Year 1 + 72 Days visits within the specified visit window, if feasible, or as close as possible to the visit window.

During the Year 1/Booster Vaccination visit, the investigator should ask the participant if he/she received any other COVID-19 vaccines and record type and date of administration.

The importance to continue practicing other public health or preventative measures that were introduced at the start of this pandemic (eg, social distancing, face masks, frequent hand washing), in compliance with local and national guidelines, will be emphasized.

## **9. STATISTICAL CONSIDERATIONS**

Statistical analysis will be done by the sponsor or under the authority of the sponsor. A general description of the statistical methods to be used to analyze the efficacy and safety data is outlined below. Specific details will be provided in the SAP.

Sections 9.1 to 9.7 are applicable to the double-blind phase of the study. Considerations for the analysis of the open-label booster vaccination phase (introduced with Amendment 6) of the study are described in Section 9.8; details will be provided in a separate SAP.

### **9.1. Statistical Hypotheses**

Refer to Section 3 for the statistical hypotheses.

The study will have the following timepoints for analysis:

1. The evaluation of the primary objective will be performed as soon as the target number of events (TNE) has been reached in the double-blind phase for both co-primary endpoints, or earlier based on sequential monitoring of both co-primary endpoints (details in Section 9.5.1). Sponsor unblinding will occur but investigator and participants remain blinded until implementation of Amendment 4 (see Section 6.4).
2. If an efficacy signal is triggered before the required 8-week follow-up after double-blind vaccination of 50% of participants is reached, an additional analysis will be performed when that follow-up timepoint is reached (8-week median follow-up timepoint). If the time between the efficacy signal and the required 8-week median follow-up is too short to make a difference in terms of preparing two analyses, then a single analysis will take place at the time of the 8-week median follow-up. The analysis at the time of the 8-week median follow-up is considered the primary analysis.
3. After the primary analysis, additional analyses to support health authority interactions will be planned, as deemed appropriate.
4. A final analysis of the double-blind phase of the study, including all double-blind data, will be performed when all participants have completed the Month 6/Unblinding Visit or

discontinued earlier. Depending on the operational implementation of the Month 6/Unblinding Visit, as well as the stage of the pandemic, this analysis may be conducted when a minimum of 90% of the study population has been unblinded.

During the open-label phase 2 possible analysis timepoints will be foreseen:

5. The open-label cross-over and booster analysis (active follow-up) can be triggered when a minimum of 90% of participants consented to Amendment 7. The timing of this analysis may be once all study sites have approved Amendment 7 or later.
6. An end-of-study analysis is planned 1 year after a minimum of 90% of the enrolled study population have reached the Year 1/Booster Visit or discontinued earlier (31 March 2023) and will be conducted upon completion of the last participant visit. Depending on the timing of approval of Amendment 7 across study sites, the 2 analysis timepoints may be combined. At the end-of-study analysis, 90% of participants will have completed one year safety follow-up; the remaining 10% of participants will have at least 6 months of safety follow-up.

Additional analyses may be conducted to support health authority interactions and/or based on public health demand in case of emerging variants.

## 9.2. Sample Size Determination

### 9.2.1. Efficacy (Total Sample Size)

The study TNE is determined using the following assumptions:

- a VE for molecularly confirmed, moderate to severe/critical SARS-CoV-2 infection of 60%.
- approximately 90% power to reject a null hypothesis of  $H_0: VE \leq 30\%$ .
- type 1 error rate  $\alpha = 2.5\%$  to evaluate VE of the vaccine regimen (employing the sequential probability ratio test [SPRT] to perform a fully sequential design analysis; detailed in Section 9.5.1).
- a randomization ratio of 1:1 for active versus placebo

Events are defined as first occurrence of molecularly confirmed, moderate to severe/critical COVID-19 according to the case definition in Section 8.1.3.1 in the PP population. The two co-primary endpoints will evaluate the events at least 14 days after double-blind vaccination (Day 15) and at least 28 days after double-blind vaccination (Day 29) with study vaccine.

Under the assumptions above, the TNE to compare the active vaccine versus placebo equals 154, based on events in the active vaccination and placebo group, according to the primary endpoints case definition of moderate to severe/critical COVID-19 (Section 8.1.3.1).

If the co-primary hypothesis testing is successful for both co-primary endpoints, secondary objectives will be evaluated against a null hypothesis employing a lower limit  $VE > 0\%$ . The

method to perform hypothesis testing of primary and secondary objectives preserving the FWER will be specified in the SAP. The FWER will be controlled at 2.5%.

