##### **9.5.1. Primary Endpoints Evaluation**

The study is designed to test the co-primary hypotheses of VE in the PP population. For both co-primary endpoints the following hypothesis will be tested:

H0: VE  $\leq 30\%$  versus H1: VE  $> 30\%$  and each hypothesis will be evaluated at a 2.5% one-sided significance level.

The co-primary endpoints will evaluate:

- the first occurrence of molecularly confirmed, moderate to severe/critical COVID-19 according to the case definition in Section 8.1.3.1, with onset at least 14 days after double-blind vaccination (Day 15) with Ad26.COV2.S versus placebo, in the PP population, including all events from both age groups, with and without comorbidities.
- the first occurrence of molecularly confirmed, moderate to severe/critical COVID-19 according to the case definition in Section 8.1.3.1, with onset at least 28 days after double-blind vaccination (Day 29) with Ad26.COV2.S versus placebo, in the PP population, including all events from both age groups, with and without comorbidities.

Participants included in the seronegative analysis set are those participants with a negative SARS-CoV-2 serology test result at (double-blind) baseline.

Considering the current COVID-19 pandemic, early detection of VE will be very important. The proposed current analysis setup is designed for continuous sequential analyses (see Section 9.5.1.1), where statistical hypothesis testing is conducted repeatedly on accumulating data, generating an earliest possible signal if and when the splits between the number of events in placebo recipients are much larger compared to the Ad26.COV2.S-vaccinated group for both co-primary endpoints and in such a way that they are unlikely to be due to chance alone using a truncated SPRT. A successful primary efficacy conclusion will require:

1. Establishing the hypothesis H1: VE  $> 30\%$  for each co-primary endpoint

AND

2. A favorable split vaccine:placebo for the subset of primary endpoints meeting the severe/critical COVID-19 case definition (expressed as a VE point estimate against severe/critical COVID-19 molecularly confirmed endpoints  $\geq 50\%$ ) and a minimum of 5 events in the placebo group. This requirement needs to be met for severe/critical events with onset at least 14 days after double-blind vaccination and for severe/critical events with onset at least 28 days after double-blind vaccination.

AND

3. A VE of at least 50% for each co-primary endpoint.

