To evaluate the primary null hypotheses: H0: VE  $\leq 30\%$  versus H1: VE  $> 30\%$  for the co-primary endpoints, the truncated sequential probability ratio test will be used based on accumulating event data for each co-primary endpoint. This boundary is set up using the fully sequential design and is derived in such a way to have approximately 90% power to detect a VE 60% using a one-sided alpha 0.025 against H0:VE  $\leq 30\%$ . For the evaluation of the favorable ratio against the severe/critical COVID-19 endpoints a sequential boundary corresponding to a VE point estimate

$\geq 50\%$  and a minimum of 5 events in the placebo group will be prespecified. The specific boundaries will be detailed in the SAP.

The monitoring can start as soon as the following conditions are met:

1. A minimum of 6 COVID-19 cases for the  $\geq 60$  years age group with onset at least 28 days after double-blind vaccination
2. At least 42 cases meeting the primary endpoints definition of moderate to severe/critical COVID-19 with onset at least 28 days after double-blind vaccination
3. A subset of at least 5 cases meeting the primary endpoints definition of severe/critical COVID-19 with onset at least 28 days after double-blind vaccination

No interim evaluation will be done, until those conditions are fulfilled. Monitoring for efficacy will not start before the above conditions 1-3 are met and will occur at least once a week by the SSG of the DSMB until the prespecified boundaries have been crossed.

The efficacy analysis will be triggered by either:

1. a) An interim evaluation if all prespecified efficacy boundaries have been met OR if 154 cases meeting the primary endpoints definition of moderate to severe/critical COVID-19 are observed for events with onset at least 28 days after double-blind vaccination

AND

1. b) The above 3 conditions are met.

OR, alternatively,

2. If the prespecified non-efficacy boundary has been met (evaluating events with start 28 days after double-blind vaccination) or when the harm boundary has been crossed. The decision rules for harm and non-efficacy are detailed in Section 9.5.1.1.

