### Sequential Probability Ratio Test

Following the notation of Dragalin et al. (2002) and Dragalin and Fedorov (2006), consider,  $X_1$  and  $X_2$  the number of events in respectively the placebo group and the vaccine group. The distribution of  $X_1$  and  $X_2$  can be approximated by a Poisson distribution with the following parameters:  $\lambda_i = n_i p_i$  (with  $i = 1,2$ ). Thus, the conditional distribution of  $X_2$  given  $T = X_1 + X_2 = t$  approximately follows a binomial distribution with parameters  $(t, \pi)$ , where  $\pi = \frac{\lambda_2}{(\lambda_1 + \lambda_2)} = \frac{n_2 p_2}{n_1 p_1 + n_2 p_2} = \frac{1 - VE}{2 - VE}$ , with  $VE = 1 - RR$ ,  $RR = \frac{p_2}{p_1}$ , assuming a vaccine group allocation ratio of 1:1. Consequently, testing the null hypothesis  $H_0: VE = VE_0$  against  $H_1: VE = VE^*$  is equivalent to testing  $H_0: \pi = \pi_0$  against  $H_1: \pi = \pi^*$  the conditional binomial test.

Consider  $\alpha = P(\text{reject } H_0 | VE = VE_0)$  and  $\beta = P(\text{accept } H_0 | VE = VE^*)$ . Rejecting  $H_0$  occurs when  $X_2 \leq C_\alpha$  with  $C_\alpha = C_\alpha(T)$  calculated to preserve  $\alpha$  over all the sequential looks such that

$P(X_2 \leq C_\alpha | \pi = \pi_0) = B(C_\alpha; T, \pi_0) \leq \alpha$ . With  $B(\cdot; T, \pi)$  the cumulative binomial distribution function with parameter  $T$  and  $\pi$ . The solution to the above equation,  $T^*$ , is the smallest  $T$  such that  $B(B^{-1}(\alpha; T, \pi_0); T, \pi^*) \geq 1 - \beta$ , with  $B^{-1}(\alpha; T, \pi)$  the  $\alpha$ -quantile of the cumulative binomial distribution function with parameters  $T$  and  $\pi$ .

The implemented critical boundaries for success are based on the truncated SPRT for which success boundaries are set based on observing  $X_2$  events on the vertical axis out of total  $T$  events on the horizontal axis.

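### The 154-event target and the printed boundary condition are single-look results, so the 2.5% error and 90% power claimed for the weekly sequential test do not follow from them

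*Protocol*

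**What the plan says.** - **Target.** Protocol 9.2.1 assumes 60% vaccine efficacy, "approximately 90% power to reject a null hypothesis of" efficacy of 30% or less, a one-sided 2.5% error rate under a fully sequential probability ratio test (SPRT), and 1:1 allocation. It concludes: "Under the assumptions above, the TNE to compare the active vaccine versus placebo equals 154".
- **Error control.** Section 9.5.1 adds that "each hypothesis will be evaluated at a 2.5% one-sided significance level". Section 9.2.1 sets the family-wise rate: "The FWER will be controlled at 2.5" (per cent).
- **Boundary.** Section 9.5.1 describes the sequential boundary as "derived in such a way to have approximately 90% power to detect a VE 60% using a one-sided alpha 0.025". Monitoring starts no earlier than 42 qualifying Day 29 cases, recurs at least weekly, and 154 such cases is itself an analysis trigger.
- **Formula.** Section 9.5.1.1, under Sequential Probability Ratio Test, says that the critical value is "calculated to preserve $\alpha$ over all the sequential looks such that" and then prints B(C_α; T, π0) ≤ α. It defines T* as the smallest T at which the power of that same one-look binomial test reaches 1 − β. It ends by saying that the implemented boundaries come from a truncated SPRT.
- **Left elsewhere.** Section 9.5.1 leaves the boundary values to the SAP. Section 9.2.1 leaves the operating characteristics to a modeling and simulation report that is to join the SAP. Neither is at hand.

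**The concern.** The sentence before the inequality promises control over all looks, while the inequality bounds the rejection probability at one value of T. Testing at a nominal 2.5% each week from 42 to 154 events is a different procedure from a sequential test with 2.5% overall. The T* formula has no term for repeated looks either, although section 9.2.1 gives 154 as the size of a fully sequential design.

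Two things are at stake for the primary efficacy claim. Whoever programs the boundary from the printed inequality gets a test with more than twice the declared error rate. Whoever holds alpha at 2.5% with an ordinary SPRT line, and stops at 154, gets less power than the protocol promises.

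**Working it through.** **Inputs.** Null efficacy 30% and alternative 60%, one-sided alpha 0.025, power 0.90, 1:1 allocation (9.2.1, 9.5.1); first look at 42 events (9.5.1). Table 8 prints a 50% null in its Day 15 efficacy row; I use 30%, as in 9.2.1 and 9.5.1. The number of events per look is not given, so I assume a look every 1, 7, 10, 14 or 20 events.

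**Step 1: reproduce 154.** With π = (1 − VE)/(2 − VE), π0 = 0.7/1.7 = 0.4118 and π* = 0.4/1.4 = 0.2857. Take the largest c with B(c; T, π0) ≤ 0.025, and find the smallest T with B(c; T, π*) ≥ 0.90.

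| T | c | level | power |
|---|---|---|---|
| 153 | 50 | 0.0191 | 0.887 |
| 154 | 51 | 0.0246 | 0.908 |

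The answer is 154 exactly. Other fixed-sample formulas give other numbers: 150 (normal approximation), 164 (Wald under the alternative), 135 (Schoenfeld), 142 (Freedman).

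**Step 2: apply the printed inequality at each look.** Exact recursion over the binomial path, 42 to 154 events, one endpoint:

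| Events between looks | Looks | Type I error | Power at VE 60% |
|---|---|---|---|
| 1 | 113 | 8.9% | 94.6% |
| 7 | 17 | 7.1% | 93.7% |
| 10 | 13 | 6.9% | 93.6% |
| 14 | 9 | 6.2% | 93.2% |
| 20 | 7 | 5.7% | 93.0% |

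**Step 3: hold alpha at 2.5% with a cap of 154.** The log-likelihood ratio is X2·ln(π*/π0) + (T − X2)·ln[(1 − π*)/(1 − π0)] = −0.3655·X2 + 0.1942·(T − X2). Rejecting when it reaches A means X2 ≤ 0.347·T − 1.787·A. Wald's constant is A = ln(0.90/0.025) = 3.584, so at T = 154 the line requires X2 ≤ 53.43 − 6.40 = 47.03, that is 47. The single-look test allows 51. That gap is where the power goes.

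| Boundary, maximum 154 events | Type I error | Power at VE 60% |
|---|---|---|
| Plain Wald line | 1.2–2.0% | 78–81% |
| SPRT line calibrated to 2.5% | up to 2.5% | 82–84% |
| Wald line, final value reset to 49 or 50 | up to 2.5% | 86–89% |
| O'Brien-Fleming-type spending | up to 2.5% | 88.5–89.3% |
| SPRT line at A = 5.3, final value 51, look at every event | 2.497% | 90.9% |

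A calibrated straight line needs about 192–197 events to reach 90% power.

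**The case against.** The strongest reply is that 2.5% and 90% are compatible with a cap of 154. That is right. An SPRT line at 5.3 with a final value of 51 gives 0.02497 and 0.9085 even with a look after every event, and at 60% efficacy it still stops before 154 events with probability 0.59. A line at 3.75, close to Wald's constant, with a final value of 50 gives 0.0247 and 0.887. A reader might infer from Step 1 that the two stated properties cannot both hold; these boundaries show that they can.

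The second reply is that the declared rule is 2.5% over all looks. Section 9.5.1.1 says so in words, its Table 8 lists control of the family-wise rate at 2.5%, and section 9.2.1 repeats it. This also stands. A reader might infer that the trial ran at 6–9% type I error; the document supports only that the printed inequality would have that property. Even then, the figure is for one endpoint. Success also needs the other co-primary endpoint, a point estimate of at least 50% on each, and the severe-case rule. Simulation with the printed inequality, assuming Day 15–28 events at 0–50% of Day 29 events, gave about 2.7–8.9% overall without the severe-case rule and 1.6–7.0% with 10–20% of cases severe.

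The third reply is that the boundaries are in the SAP. This limits what can be said about the real power, but not about the protocol's own text, which prints the formula, the target, the alpha and the power, and makes 154 a trigger. One route is unaffected: section 9.5.1 allows a single analysis at the full 2.5% if 154 is passed before the monitoring conditions are met, and there the single-look calculation is the right one.

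**Conclusion.** The point holds as an error in what the protocol prints. The displayed condition contradicts the sentence that introduces it; used at each look it gives about 5.7–8.9% type I error per co-primary endpoint. The figure of 154 is the fixed-sample exact binomial number, and it is wrongly presented, with its 90% power, as a property of the fully sequential test.

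With alpha held at 2.5%, power at 154 events runs from about 78% to 91% according to boundary shape. The claim of approximately 90% is thus attainable, but the formula does not establish it, and an ordinary SPRT line falls 6 to 12 points short. A reader might go further and take some one value in the low eighties as the trial's real power. The protocol does not support that, because the line constant and the final value are not in it.

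These figures concern rejection of the 30% null on one endpoint. They rest on the assumed look spacing and on the conditional binomial model of section 9.5.1.1.

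**What to change.** 1. In section 9.5.1.1, replace the inequality by the cumulative constraint P(X2(T) ≤ C(T) at any look T | π0) ≤ 0.025.
2. In sections 9.2.1 and 9.5.1.1, state that 154 is the fixed-sample number and serves as the truncation point. Say how the critical value is chosen: with the largest c whose level is at most 2.5% the formula gives 154, while the usual quantile convention lets the level exceed 2.5% and gives 138.
3. In sections 9.2.1 and 9.5.1, report type I error and power for the truncated boundary actually used, with its look schedule. Either choose a boundary that keeps about 90% at 154, or restate the power.

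The cost is protocol wording and one exact recalculation. No participants are added if 154 is kept. A boundary that is strict early makes early stopping somewhat less likely: at 60% efficacy, 0.59 for the line at 5.3 against 0.79 for the line at 3.75.
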